6.13.1 Performing Adverse Events Assessments

During the course of the study, and maximum 30 days after the last dose of study drug, if hospital discharge has not occurred, the Investigator or designee will routinely monitor and solicit each patient for the occurrence of any AEs. If an AE occurs, a full description of the event, including the date and time of onset, duration, severity, actions taken, outcome, seriousness of the event, and causal relationship of the AE to the study treatment will be recorded in the patient's CRF. All AEs will be followed by the Investigator until the event has resolved, stabilized, or returned to baseline.

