5.6.4 Patient Activity Restrictions

Patients will remain hospitalized while enrolled in the study.

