6.13.7.2 Reporting Serious Adverse Events

All SAEs or any pregnancy reports with or without an associated SAE must be reported to the sponsor within 24 hours of site's knowledge of the event. Further details are specified in the Safety Management Plan.

The Investigator will also report any SAEs to the Institutional Review Board (IRB) in writing based on the IRB's reporting requirements and provide the Sponsor with a copy of the notification.

All SAEs including follow-up information that occur from the date of signing of ICF until 30 days after the last dose of study treatment must be reported to Baxter Global Pharmacovigilance.

Baxter or designee will assess each SAE reported by the Investigator to determine if the event qualifies as an Expedited Report according to local regulations. Expedited reports will be submitted to the appropriate Authority by Baxter or designee. Per regulations, Investigators will receive a letter from Baxter or designee describing the expedited SAE. The Investigator should file this letter within their Investigator Site File. Additionally, the Expedited Report letter may need to be submitted by the Investigator to their IRB, as appropriate per local regulations.

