6.13.8 Treatment-Emergent Adverse Events

A treatment-emergent AE is defined as any AE that occurs after the onset of study treatment administration through the end of the study.

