6.14 Removal of Patients from the Study/ Discontinuation of the Study

Any patient/legal representative may voluntarily withdraw consent for continued participation and data collection at any time during the course of the study. The Investigator may terminate a patient's study participation at any time during the study if the Investigator judges it to be in the patient's best interest.

Patients may be withdrawn or prematurely discontinued from the study treatment/assessments for any of the following reasons:

- Adverse Event(s)
- Clinically significant change in a laboratory parameter
- Protocol violation (i.e. patient failed to meet protocol entry criteria or did not adhere to the protocol requirements)
- Pregnancy
- Patient or any legal representative requests to withdraw from the study
- Sponsor or Investigator terminates the study

All patients randomized to Clinolipid who must receive Intralipid for rescue therapy purposes will be discontinued from the trial.

Parenteral nutrition therapy may be interrupted and restarted (based on the initial randomization) within a 1 to 2-day window, subject to adjudication from the medical monitor who conducts a clinical review of current patient status, assessment of any potential AE/SAEs, discussion/clarification with the investigator to resume or abort study treatment. The outcome of the adjudication process will not preclude the monitoring for AE/SAEs for the subsequent 30 days and in the event of an AE, following the subject until the AE resolves, stabilizes or the subject returns to baseline. If there is a likelihood that the patient will require restart of PN within 1 to 2 days of the initial stoppage, then it is recommended to delay performing the End of Study Treatment procedures. However, the End of Study Treatment procedures should be completed within 2 days of the initial stoppage if the patient has not restarted PN, as per Section 7.2.4 and Appendix 1 Schedule of Events.

If a patient's participation is discontinued, the reason(s) must be recorded in the source documents and in the CRF.

End of study treatment procedures should be performed when a patient withdraws or is discontinued from the study.

Patients who are withdrawn from the study will not be replaced.

The study may be discontinued:

- If new safety information becomes available indicating that continuing the study treatment or procedures may jeopardize the safety of the patients
- Because of an administrative decision by the Sponsor

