- ^k Parenteral nutrition therapy may be interrupted and restarted (based on the initial randomization) within a 1 to 2-day window, subject to adjudication from the medical monitor who conducts clinical review of current patient status, assessment of any potential AE/SAEs, discussion/clarification with investigator to resume or abort study treatment. If there is a likelihood that the patient will require restart of PN within 1 to 2 days of the initial stoppage, then it is recommended to delay performing the End of Study Treatment procedures. However, the End of Study Treatment procedures should be completed within 2 days of the initial stoppage if the patient has not restarted PN.

Evaluation	Evaluation Screening Baseline	Baseline ^a	ie ^a Daily	Study Treatment Day (every 15 days ±2 days)					End of Study Treatment ^o
				15	30	45	60	75	or Day 90 (± 2 days)

¹ When breastfeeding intakes cannot be measured, the best estimation (volume) of the investigator will be recorded.

^mMedications and nutrition supplements received within 30 days prior to randomization by the patient and the nursing mother (if applicable) also will be recorded at Screening. The nursing mother's medication history will be collected from the patient's chart (if available).

ⁿ Adverse events occurring prior to the initiation of the first study procedure will be recorded as signs and symptoms in the patient's medical history. During the course of the study, and for 30 days after the last dose of study drug, the Investigator or designee will routinely monitor and solicit each patient for the occurrence of any AEs. All SAEs or any pregnancy reports with or without an associated SAE must be reported to Baxter Global Pharmacovigilance within 24 hours of site's knowledge of the event.

^o End of study treatment is defined as the last day of PN with Intralipid or Clinolipid; maximum 90 days of study treatment is allowed. After 90 days, the patient will receive nutritional intervention as prescribed by their healthcare provider if still required.

Fatty Acid	Chain Length	Reference Values
Lauric Acid	C12:0	<1 year: 6-190 nmol/mL
		1-17 years: 5-80 nmol/mL
		> or =18 years: 6-90nmol/mL
Myristic Acid	C14:0	<1 year: 30-320 nmol/mL
		1-17 years: 40-290 nmol/mL
		> or =18 years: 30-450 nmol/mL
Hexadecenoic Acid	C16:1n-9	<1 year: 21-69 nmol/mL
		1-17 years: 24-82 nmol/mL
		> or =18 years: 25-105 nmol/mL
Palmitoleic Acid	C16:1n-7	<1 year: 20-1,020 nmol/mL
		1-17 years: 100-670 nmol/mL

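### Protocol 6.13.1 stops soliciting AEs at hospital discharge, but the schedules in both documents require 30 days for every patient, so the recorded number of late non-serious AEs depends on which text a site follows

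*Protocol*

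**What the plan says.** Four places set how long AEs are sought after the last dose.

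- **Protocol 6.13.1**, the main instruction for AE assessment, limits solicitation to a "maximum 30 days after the last dose of study drug, if hospital discharge has not occurred".
- **Protocol Appendix 1, footnote n**, says that "for 30 days after the last dose of study drug, the Investigator or designee will routinely monitor and solicit each patient". It does not mention discharge. Footnote n in SAP 1.4.5 repeats it.
- **Protocol 6.14**, on adjudication after PN is interrupted, says that the outcome "will not preclude the monitoring for AE/SAEs for the subsequent 30 days", again without a discharge condition.
- **Protocol 6.13.7.2** has a separate rule for serious events, which run "from the date of signing of ICF until 30 days after the last dose of study treatment" whether or not the patient has gone home.

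The definitions that decide what is tabulated are open at the far end. Protocol 6.13.8 defines a treatment-emergent AE as "any AE that occurs after the onset of study treatment administration through the end of the study", with no day count. SAP 2.5.1.1 gives a start (first study treatment) and no end. SAP section 3 reports no changes from the protocol and does not choose a window.

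**The concern.** A site cannot follow both 6.13.1 and footnote n for a patient who goes home soon after PN stops. Under the first text, routine solicitation ends at discharge. Under the second, it continues to day 30 after the last dose. New non-serious AEs starting in that gap are collected or not according to the page the site works from.

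Safety is one of the three secondary endpoints and is reported as the number and percentage of patients with an event, plus a rate per 100 patient days. A percentage makes no allowance for unequal observation time. The AESI list in Protocol 2.2 also includes delayed reactions to lipid emulsions, such as hepatomegaly, jaundice and thrombocytopenia. The non-serious forms of these could be missed if solicitation stops at discharge.

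Under 6.13.1 the cut-off is also a post-randomization event. Patients who recover and leave sooner are observed for less time.

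**Working it through.** The plan gives no figure to reproduce: the sample size rests on feasibility and no AE rate is assumed. The check compares the windows and then sizes the gap.

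**Windows compared**

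| Patient | 6.13.1 | Footnote n (both documents) | SAEs (6.13.7.2) |
|---|---|---|---|
| Discharged on the last day of PN | 0 days after last dose | 30 days | 30 days |
| Discharged d days later, d < 30 | d days | 30 days | 30 days |
| Still in hospital at day 30 | 30 days | 30 days | 30 days |

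The conflict is confined to the first two rows and to non-serious events.

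**Observation time.** Let T be days on treatment (Protocol 5.2: 7 up to 90) and d the days from last dose to discharge. The documents give no discharge times, so d is an assumption. The ratio of footnote n to 6.13.1 is (T + 30)/(T + d).

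- d = 0, T = 7: 37/7 = 5.3
- d = 0, T = 20 (an illustrative value, not from the documents): 50/20 = 2.5
- d = 0, T = 90: 120/90 = 1.33
- d = 10, T = 7: 37/17 = 2.2
- d = 10, T = 90: 120/100 = 1.2
- d = 30, any T: 1.0

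**Effect on what is reported.** This step needs an assumed AE rate, taken as constant on and off treatment.

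*Percentage with at least one AE*, at 1 event per 100 days, is 1 − exp(−0.01 × days observed):

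| T | Treatment days only | Plus 30 days |
|---|---|---|
| 7 | 6.8% | 30.9% |
| 15 | 13.9% | 36.2% |
| 30 | 25.9% | 45.1% |
| 90 | 59.3% | 69.9% |

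*Rate per 100 patient days.* Protocol 9.6.3 and SAP 2.5.1.1 divide by treatment days only, while the SAP definition of a TEAE lets later events into the numerator. At an assumed 10 events per 100 days, the reported rate is 10 × (T + D)/T, where D is the number of post-treatment days solicited. With D = 0 it is 10.0 at every T. With D = 30 it is 52.9 at T = 7, 30.0 at T = 15, 20.0 at T = 30 and 13.3 at T = 90.

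All these contrasts are upper bounds if the AE hazard falls after treatment or after discharge.

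**The case against.** The strongest reply is that the scope is narrow and the cause is wording. Protocol 5.6.4 says "Patients will remain hospitalized while enrolled in the study", which gives 6.13.1 a sensible reading: solicitation ends when the patient leaves, and footnote n may simply abbreviate that rule. SAEs run to 30 days in any case, and 6.13.1 follows AEs already recorded until they resolve, stabilize or return to baseline. This stands as a limit on scope. It does not remove the conflict, because footnote n names each patient without condition in both documents.

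A reader might infer that the AE comparison between arms is biased. The documents do not support that. Randomization is stratified by site (Protocol 5.4), and investigators and site personnel are blinded (5.5), so a site's reading applies to both arms. Bias would need discharge timing to differ by arm, and nothing in the documents shows this. The study is descriptive, with no formal testing and with sites pooled (SAP 1.4.2, 2.6.3, 2.6.4).

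A reader might also take the 5.3-fold figure as typical, or as a ratio of AE counts. It is neither. It is a ratio of observation time for a patient treated for 7 days and discharged on the last day of PN.

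Finally, a table that ends at the end-of-treatment visit also ends at a post-randomization event, since PN may stop because oral or enteral feeding has become adequate. That is correct and limits what the remedy achieves.

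**Conclusion.** The contradiction is in the current text and nothing else in either document resolves it. For patients discharged within 30 days of the last dose, recording of new non-serious AEs depends on which passage a site follows. Because the TEAE definitions have no day limit, those events change the reported percentages and rates. The SAE reporting window is unaffected.

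The ratio of observation time lies between 1.0 and 5.3. The upper end assumes the shortest intended treatment and discharge on the last day of PN. What is established is an inconsistency in absolute AE counts and between sites; a distorted comparison between arms remains conditional on discharge timing differing by arm. The point should be corrected, but it does not undermine the primary endpoint.

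**What to change.** 1. State one AE collection window, in the same words, in Protocol 6.13.1, 6.14 and Appendix 1 footnote n, and in SAP 1.4.5 footnote n.
2. Give the TEAE definition in Protocol 6.13.8 and SAP 2.5.1.1 an end date that matches it.
3. Base the main TEAE table on first dose through the end-of-treatment visit. Protocol 7.2.4 schedules that visit for every patient within 2 days of the last day of treatment, and 6.14 asks for it on withdrawal, so the period closely matches the treatment-days denominator.
4. Tabulate later events separately, by discharge status.

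The cost is wording in two documents and one extra table. Keeping 30 days for everyone requires contact after discharge; footnote n already implies this, but the schedule lists no visit or call for it, so one would have to be added. Choosing the shorter window avoids that and loses some late non-serious AEs. The main table will still cover a period that varies with time on PN, so its percentages should be read beside the rate per 100 patient days.

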6.13.2 Severity

The severity of an AE is defined as a qualitative assessment by the Investigator of the degree of intensity of the AE observed or reported by the patient. The assessment of severity will be made irrespective of treatment relationship or seriousness.

The severity of each AE will be recorded as mild, moderate, or severe according to the following definitions:

- Mild The AE is a transient discomfort and does not interfere in a significant manner with the patient's normal functioning level and/or the AE resolves spontaneously or may require minimal therapeutic intervention.
- Moderate The AE produces limited impairment of function and may require therapeutic intervention and/or the AE produces no sequela/sequelae.
- Severe The AE results in a marked impairment of function and may lead to temporary inability to resume usual life pattern and/or the AE produces sequela/sequelae, which require (prolonged) therapeutic intervention.

6.13.3 Relationship

Causality is a determination of whether there is a reasonable possibility that the investigational product/control is etiologically related to/associated with the AE. Causality assessment includes, for example, assessment of temporal relationships, dechallenge/rechallenge information, association (or lack of association) with underlying disease, presence (or absence) of a more likely cause, and physiologic plausibility For each AE, the investigator will assess the causal relationship between the investigational product (IP) / control and the AE using his/her clinical expertise and judgment according to the following most appropriate algorithm for the circumstances of the AE:

- Not related (both circumstances must be met).
- a. Is due to underlying or concurrent illness, complications, concurrent treatments, or effects of concurrent drugs.
- b. Is not associated with the IP/control (i.e., does not follow a reasonable temporal relationship to the administration of IP/control or has a much more likely alternative aetiology).
- Unlikely related (either 1 or both circumstances are met).
 - a. Has little or no temporal relationship to the IP/control.
 - b. A more likely alternative aetiology exists.
- Possibly related (both circumstances must be met).
 - a. Follows a reasonable temporal relationship to the administration of IP/control.
 - b. An alternative aetiology is equally or less likely compared to the potential relationship to the IP/control.
- Probably related (both circumstances must be met).
 - a. Follows a strong temporal relationship to the administration of IP/control, which may include but is not limited to the following:
 - 1. Reappearance of a similar reaction upon re-administration (positive re-challenge).
 - 2. Positive results in a drug sensitivity test (skin test, etc.).
 - 3. Toxic level of the IP/control as evidenced by measurement of the IP/control concentrations in the blood or other bodily fluid.
 - b. Another aetiology is unlikely or significantly less likely.

6.13.4 Expectedness

A suspected unexpected serious adverse reaction (SUSAR) is any adverse reaction that is classified as serious and is suspected to be caused by the investigational drug but is not consistent with the information found in the current version of the Investigator's Brochure.

6.13.5 Clinical Significance

Clinical significance of AEs will be determined by the Investigator, based on his/her best medical judgement.

6.13.6 Clinical Laboratory Adverse Events

Laboratory and vital sign abnormalities qualify as AEs if medical intervention is required to treat or address the abnormality, if patients must be discontinued from the study due to the abnormality or if the value exceeds specific limits qualifying it as an AE.

6.13.7 Serious Adverse Events

6.13.7.1 Definition

A SAE is defined by federal regulation as any AE occurring at any dose that results in any of the following outcomes: death, life-threatening, inpatient hospitalization or prolongation of existing hospitalization, persistent or significant disability/incapacity or congenital anomaly/birth defect.

Important medical events that may not result in death, be life threatening, or require hospitalization may be considered an SAE when, based upon appropriate medical judgement, they may jeopardize the patient and may require medical or surgical intervention to prevent one of the outcomes listed in this definition. Examples of such medical events include allergic bronchospasm requiring intensive treatment in an emergency room or at home, blood dyscrasias or convulsions that do not result in inpatient hospitalization, or the development of drug dependency or drug abuse.

6.13.7.2 Reporting Serious Adverse Events

All SAEs or any pregnancy reports with or without an associated SAE must be reported to the sponsor within 24 hours of site's knowledge of the event. Further details are specified in the Safety Management Plan.

The Investigator will also report any SAEs to the Institutional Review Board (IRB) in writing based on the IRB's reporting requirements and provide the Sponsor with a copy of the notification.

All SAEs including follow-up information that occur from the date of signing of ICF until 30 days after the last dose of study treatment must be reported to Baxter Global Pharmacovigilance.

Baxter or designee will assess each SAE reported by the Investigator to determine if the event qualifies as an Expedited Report according to local regulations. Expedited reports will be submitted to the appropriate Authority by Baxter or designee. Per regulations, Investigators will receive a letter from Baxter or designee describing the expedited SAE. The Investigator should file this letter within their Investigator Site File. Additionally, the Expedited Report letter may need to be submitted by the Investigator to their IRB, as appropriate per local regulations.

6.13.8 Treatment-Emergent Adverse Events

A treatment-emergent AE is defined as any AE that occurs after the onset of study treatment administration through the end of the study.

6.14 Removal of Patients from the Study/ Discontinuation of the Study

Any patient/legal representative may voluntarily withdraw consent for continued participation and data collection at any time during the course of the study. The Investigator may terminate a patient's study participation at any time during the study if the Investigator judges it to be in the patient's best interest.

Patients may be withdrawn or prematurely discontinued from the study treatment/assessments for any of the following reasons:

- Adverse Event(s)
- Clinically significant change in a laboratory parameter
- Protocol violation (i.e. patient failed to meet protocol entry criteria or did not adhere to the protocol requirements)
- Pregnancy
- Patient or any legal representative requests to withdraw from the study
- Sponsor or Investigator terminates the study

All patients randomized to Clinolipid who must receive Intralipid for rescue therapy purposes will be discontinued from the trial.

Parenteral nutrition therapy may be interrupted and restarted (based on the initial randomization) within a 1 to 2-day window, subject to adjudication from the medical monitor who conducts a clinical review of current patient status, assessment of any potential AE/SAEs, discussion/clarification with the investigator to resume or abort study treatment. The outcome of the adjudication process will not preclude the monitoring for AE/SAEs for the subsequent 30 days and in the event of an AE, following the subject until the AE resolves, stabilizes or the subject returns to baseline. If there is a likelihood that the patient will require restart of PN within 1 to 2 days of the initial stoppage, then it is recommended to delay performing the End of Study Treatment procedures. However, the End of Study Treatment procedures should be completed within 2 days of the initial stoppage if the patient has not restarted PN, as per Section 7.2.4 and Appendix 1 Schedule of Events.

If a patient's participation is discontinued, the reason(s) must be recorded in the source documents and in the CRF.

End of study treatment procedures should be performed when a patient withdraws or is discontinued from the study.

Patients who are withdrawn from the study will not be replaced.

The study may be discontinued:

- If new safety information becomes available indicating that continuing the study treatment or procedures may jeopardize the safety of the patients
- Because of an administrative decision by the Sponsor

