6.8.3 Holman Index >0.4

Patients with Holman index >0.4 will be considered as biochemical EFAD. It will be confirmed in the context of low LA, low ARA, and high eicosatrienoic acid (Mead acid).

Clinical EFAD is diagnosed in the presence of any clinical features of EFAD (dermatitis, diarrhea, perianal irritation, growth and development failure, recurrent infections, irritability, and/or poor wound healing).

The management of these patients includes the assessment, the record, and the increase of LA intakes until the Holman Index normalizes and clinical features, if present, disappear.

The daily monitoring of LA intakes, and the approximately every 15 day monitoring of LA and ARA levels and Holman Index will persist until the Holman Index normalizes and clinical features disappear. If the Holman Index does not reduce to <0.4 or if it continues to increase, lipid intake will be further increased. The amount of the increase in LA intake should be determined by the clinician considering the clinical state of the patient and the safety of increasing the total lipid intake.

Some patients may have higher requirements for EFAs due to an underlying disease (e.g. high demand for growth and wound healing). Total parenteral lipid intake should usually remain below the maximum intake (Table 4, Dosing Schedule), which is an amount that is normally adequate for prevention of EFAD in all patients. The patient should receive the increased LA intake for at least 1 week prior to repeating the FA profile with the Holman Index assessments to allow time for the physiologic effects of the FA to occur.

When EFAD persists despite maximal lipid intake, the ILE should be unblinded. If the patient is receiving Clinolipid, the patient should be switched to Intralipid to allow for greater delivery of LA.

Additional LA intakes may be supplied via intravenous and/or enteral/oral routes.

If severe hypertriglyceridemia (triglycerides >400 mg/dL) develops, the cause should be investigated. If it is determined to be related to the ILE, lipid intake may be adjusted using the ILE with the higher relative content of LA.

If direct bilirubin increases above 2.5 mg/dL suggestive of cholestasis, a reduction of total lipid intake may be considered while continuing to provide adequate LA. The adequacy of LA intake needs to be confirmed by the unblinded pharmacist(s).

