6.8.4 Holman Index >0.4 at baseline

Some study patients (especially premature infants) may demonstrate FA profile and Holman index compatible with EFAD at baseline due to their limited fat stores. The treatment for these infants is to administer EFA via ILE as part of their PN as described in Table 4, Dosing Schedule and being sure to reach the maintenance dosage. Infants with EFAD at baseline are to be followed regularly (approximately every 15 days) while receiving ILE per study protocol for improvement in their FA profile and Holman Index.

• If the Holman Index does not decrease with lipid administration in accordance with Table 4, Dosing Schedule, the patient may have greater than normal

requirements for EFA and the LA intake should be increased to the maximum dosage according to Table 4, Dosing Schedule and at the investigator's discretion.

- If the patient still does not respond, the investigator will be unblinded to determine if the patient is receiving Clinolipid or Intralipid. If the patient is receiving Clinolipid, the patient should be switched to Intralipid (as Intralipid contains a higher concentration of LA than Clinolipid).
- If the patient does not respond to Intralipid at maximal lipid dosage, consider increasing the LA intake with an enteral/oral source of LA or some additional intravenous Intralipid intakes.

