2.6.2 Handling of Dropouts or Missing data

All data collected up to the point where the patient drops out will be used for analyses.

Aside from missing weight in the calculation of nutritional intake, no missing data will be imputed for this study.

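### Protocol 6.14 takes only rescued Clinolipid patients out of the trial, which does not sit with 6.8.3, 6.8.4 and 7.2.4, so later follow-up data are lost in one arm

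*Protocol*

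**What the plan says.** - **Protocol 6.14:** "All patients randomized to Clinolipid who must receive Intralipid for rescue therapy purposes will be discontinued from the trial". This is mandatory and names one arm. The other withdrawal reasons in 6.14 are optional and cover both arms. End-of-treatment procedures are done at discontinuation.
- **Protocol 6.8.3 (Holman Index above 0.4):** "When EFAD persists despite maximal lipid intake, the ILE should be unblinded", in either arm. Then: "If the patient is receiving Clinolipid, the patient should be switched to Intralipid to allow for greater delivery of LA". The section also says that "approximately every 15 day monitoring of LA and ARA levels and Holman Index will persist until the Holman Index normalizes and clinical features disappear", and it sets no end to this at the switch. Discontinuation is not mentioned.
- **Protocol 6.8.4 (above 0.4 at baseline):** the same switch for non-responders, followed by a further step: "If the patient does not respond to Intralipid at maximal lipid dosage, consider increasing the LA intake with an enteral/oral source of LA". Again there is no mention of discontinuation.
- **Protocol 7.2.4:** study treatment ends on the last day of PN with either of the two products, up to 90 days.
- **Protocol 9.3:** unblinded infants are to be analysed separately.
- **SAP 2.6.2:** "All data collected up to the point where the patient drops out will be used for analyses". Nothing is imputed except missing weight for nutritional intake. SAP 2.1.3 lists no discontinuation reason for a rescue switch. The SAP contains no separate analysis of unblinded infants, although its Section 3 declares no change from the protocol.

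**The concern.** A site with a Clinolipid patient whose EFAD persists at maximal lipid intake gets two signals. Section 6.14 ends trial participation at the switch. Sections 6.8.3 and 6.8.4 read as though the patient is still being assessed. An Intralipid patient in the same state is also unblinded, but can receive additional linoleic acid and remain in scheduled follow-up.

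If 6.14 prevails, the patients who did worst on Clinolipid leave the later visits and their counterparts on Intralipid do not. Later Clinolipid rows are then based on a selected group. In a descriptive study whose subject is EFAD risk, these few patients are among the most informative.

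**Working it through.** The plan gives no expected number of switches, so there is no figure of that kind to reproduce. The only related figure is the sample size, 50 + 50 = 100, set by feasibility.

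**1. The two arms side by side, for EFAD persisting at maximal lipid intake**

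| | Clinolipid | Intralipid |
|---|---|---|
| Unblinded (6.8.3) | yes | yes |
| Change of emulsion (6.8.3) | to Intralipid | none |
| Mandatory discontinuation (6.14) | yes | no |
| Later scheduled assessments | stop under 6.14; implied to continue under 6.8 | continue |

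**2. The end date.** A switched patient is still on PN with Intralipid. Under 7.2.4, study treatment can be read as ongoing; under 6.14 the patient is out of the trial. The date matters in the SAP: person-time for PNALD (2.4.2.2.1) and for adverse event rates (2.5.1.1) runs to the end date of treatment.

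**3. The primary endpoint.** SAP 2.4.1.1 counts a patient once, at the first Holman Index above 0.4 on treatment, and stops that patient's person-time there. A 6.8.3 switch requires EFAD that has already persisted, so it comes after the event. With k such patients among 50, the proportion is k/50 with or without the rule: 2%, 4%, 6% or 10% for k = 1, 2, 3 or 5 (values of k assumed).

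**4. Scheduled data forgone.** Post-baseline fatty acid samples fall on Days 15, 30, 45, 60, 75 and 90. For a switch on day s in a patient whose PN would have run to Day 90:
- days forgone = 90 − s
- samples forgone = number of scheduled days later than s

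The value s = 22 is the Day 15 sample plus the one-week minimum in 6.8.3 ("The patient should receive the increased LA intake for at least 1 week prior to repeating the FA profile"), 15 + 7. The others are scheduled visit days.

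| Switch day s | Days forgone | Samples forgone, of 6 |
|---|---|---|
| 22 | 68 | 5 |
| 30 | 60 | 4 |
| 45 | 45 | 3 |
| 60 | 30 | 2 |

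These are upper limits, because many patients would stop PN before Day 90. The end-of-treatment sample partly offsets the loss, but it shows status at the switch, not the response to it. SAP 2.1.2 places it in a combined Day 90/end-of-treatment row, so it need not fill the missed interim visits.

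**5. Person-time (assumed inputs).** Take 50 Clinolipid patients. All but k stay 30 days; the k cases would stay 90 but stop at Day 30. Full person-time is (50 − k) × 30 + k × 90; truncated, it is 50 × 30 = 1500.
- k = 1: 1560 to 1500, a loss of 3.8%
- k = 2: 1620 to 1500, a loss of 7.4%
- k = 3: 1680 to 1500, a loss of 10.7%
- k = 5: 1800 to 1500, a loss of 16.7%

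Events in the lost time go too, so this sizes the lost exposure and not a bias in the rate.

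**The case against.** **The sections can be followed together.** In 6.8.3 the monitoring sentence precedes the switch sentence and concerns patients whose linoleic acid intake is being raised. In 6.8.4, non-response to Intralipid also fits a patient who is unblinded and found to have been on Intralipid throughout. Section 6.8 governs care and 6.14 governs participation. This largely stands: a reader might infer that the protocol schedules Holman samples after the switch, but it only implies them. The sections still leave a site unsure, and 7.2.4 adds to that.

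**The asymmetry is structural.** Only Clinolipid patients can cross to the other study product. This explains a one-sided change of treatment. It does not require one-sided data collection.

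**Section 9.3 already separates unblinded infants in both arms.** This is true of the protocol's intention, but it covers infants only and the SAP does not carry it out.

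Three stronger readings are tempting and are not supported:
- *The primary result is biased.* The event is recorded before a 6.8.3 switch, so the proportion, rate and time to EFAD barely change.
- *The outcome of these patients goes unrecorded.* End-of-treatment procedures include the fatty acid profile, Holman Index, liver tests and growth. The high value also enters the summary at the maximum (SAP 2.4.1.2). Protocol 6.13.1 solicits adverse events for up to 30 days after the last dose while the patient is in hospital, and follows them to resolution or stabilisation. What is missing is serial Holman values after the switch.
- *The later Clinolipid Holman mean is understated by a known amount.* That needs the number of switches and the course of the index after the switch. The documents give neither, and a response to Intralipid would lower the later values anyway.

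**Conclusion.** The point holds in a limited form. Section 6.14 imposes trial discontinuation on rescued Clinolipid patients alone. It is not reconciled with 6.8.3, 6.8.4 and 7.2.4, and SAP 2.6.2 leaves the later data missing on one side. The loss falls on later by-visit Holman and fatty acid summaries and on PNALD, liver, growth and intake data. The primary first-event analyses are little affected.

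For an individual patient the loss can be large: up to 5 of 6 scheduled fatty acid samples for a switch at Day 22, if PN would have lasted to Day 90. Across the arm the size is unknown and probably small, because a switch needs EFAD that persists at maximal lipid intake or baseline EFAD that does not respond. No hypothesis test depends on it. It is worth correcting because correction is cheap. No view is taken on whether or when a patient should be switched.

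**What to change.** **Protocol.** Reconcile 6.8.3, 6.8.4, 6.14 and 7.2.4. Define the end of randomised treatment separately from the end of data collection. Continue the scheduled assessments to the end of PN or Day 90 for every patient in both arms, and record the switch date.

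**SAP.**
- State which date is the end date of treatment for a switched patient in the person-time formulas.
- Report by-visit summaries by randomised arm both with and without post-switch values. Both are needed, because values after the switch reflect Intralipid and could flatter the Clinolipid arm if rescue works.
- Carry over the separate analysis of unblinded infants promised in Protocol 9.3, or declare the change in SAP Section 3.

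**Cost.** A protocol clarification, a SAP revision, and a few additional fatty acid and phytosterol samples in patients who are still inpatients on PN. The fatty acid samples carry the 4-hour lipid hold in Protocol 6.7.2.4, and 6.15 describes phytosterol testing as non-standard, so this is not wholly routine care. The number of patients involved should be small.
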